The duration of study participation will be 108 weeks, including screening and post-randomization. Following screening, subjects must be randomized within 28 days. Following randomization there will be a 52-week treatment period with study agent followed by a 52-week off-therapy follow-up period.

Responders at Week 52 who are still in the follow-up period and who are determined to be in the active treatment group will have the option to restart active therapy while the non-responders will continue to follow the originally planned study design, ie, the off-therapy follow-up monitoring period.

There will be an open-label extension period of the study for responders. Responders are defined as subjects who have profile at Week 52 which includes:

1. C-peptide and Remission score* responders (C+R responders): either having an increase in C-peptide AUC versus baseline or having a stable C-peptide AUC, not decreasing more than 5% versus baseline and having a remission score ≤ 9 .
OR
2. C-peptide responders (C responders): either having an increase in C-peptide AUC versus baseline or having a stable C-peptide AUC, not decreasing more than 5% versus baseline but not meeting a remission score of ≤ 9 . Their remission score, however, must be < 12 .
OR
3. Remission score responders (R responders): having a remission score ≤ 9 but not meeting C-peptide response as defined above. However, their C-peptide AUC decline from baseline should be less than or equal to 30% compared to baseline.

*Insulin Dose Adjusted HbA1c: IDAA1c= A1C (percent) + [4 × insulin dose (units per kilogram per 24 h)].

This study will enroll male and female subjects 6 through 21 years of age who have been recently diagnosed with T1D and are able to be randomized within 100 days of diagnosis. A target of approximately 81 subjects will be randomly assigned in a 2:1 ratio to receive golimumab or placebo, administered SC for 52 weeks and monitored for an additional 52 weeks. Subjects will be randomized to receive active therapy (golimumab) or placebo and be stratified based on C-peptide AUC levels of < 0.66 pmol/mL or ≥ 0.66 pmol/mL from a 4-hour MMTT conducted at study screening. The protocol will give the option for study agent administration by the subject or caregiver outside of the study site, ie, self-administration, after proper training.

An independent Data Monitoring Committee will be commissioned to continually assess the safety of study subjects.

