2. OBJECTIVES, ENDPOINTS, AND HYPOTHESIS

2.1. Objectives and Endpoints

- Double-Blind Period

Objectives	Endpoints
Primary Objective and Endpoints	

 • To determine if golimumab can preserve β-cell function in children and young adults with newly diagnosed T1D. 	
 • The Mixed-meal Tolerance Test (MMTT) - stimulated 4-hour C-peptide area under the concentration-time curve (AUC) at Week 52.
Secondary Objectives and Endpoints: Efficacy	

 • To evaluate the impact of golimumab on measures of diabetes control in this subject population. • To evaluate the off-therapy durability of golimumab on measures of diabetes control in this subject population. 	
 • Change from baseline in insulin use in units per kilogram body weight per day over time. • Change from baseline in HbA1c over time. • Hypoglycemic event rates (defined as BG of ≤ 70, 55, and 35 mg/dL or clinical sequelae in the absence of a BG reading) through Week 52, after Week 52 through Week 104, and the entire study. • MMTT-stimulated 4-hour C-peptide AUC over time.

Objectives	Endpoints
Secondary Objective and Endpoints: Safety	

 To determine the safety and tolerability of golimumab in children and young adults with T1D. 	
 Proportion of participants with treatment-emergent AEs and severe AEs through Weeks 52 and 104. Proportion of participants with severe infections through Weeks 52 and 104. Proportion of participants with study agent injection site reactions through Week 52.
Secondary Objective and Endpoints: Pharmacokinetics (PK) and Immunogenicity	

 To evaluate the PK and immunogenicity of golimumab in this specific subject population with T1D. 	
 Summary of serum golimumab concentrations and the PK profile after induction and maintenance dosing. Incidence and titers of antibodies to golimumab.
Exploratory Objective and Endpoints: Immunologic and Metabolic	

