Note: If the childbearing potential changes after start of the study (eg, female who is not heterosexually active becomes active, premenarchal female experiences menarche) she must begin a highly effective method contraception of birth control, as described throughout the inclusion criteria.

- Agrees to remain on a highly effective method of birth control throughout the study.
7. During the treatment period of the study (from randomization through Week 52) and for a minimum of 1 spermatogenesis cycle (defined as 90 days after receiving the last dose of study agent), all males must:
- Agree to be sexually abstinent or (2) if sexually active with a non-pregnant female of childbearing potential must agree to use a barrier method of contraception (eg, condom with spermicidal foam/gel/film/cream/suppository) and if sexually active with a female who is pregnant must use a condom.
 - Agree not to donate sperm.
8. Subjects (or their legally acceptable representatives) are willing and able to adhere to requirements, prohibitions, and restrictions specified in this protocol.
9. Subjects (or their legally acceptable representative) must sign an ICF indicating that he or she understands the purpose of, and procedures required for, the study and is willing to participate in the study. Assent is also required of children capable of understanding the nature of the study (typically 7 years of age and older) as described in Section 16.2.3, Informed Consent and Assent Form.

10. Subjects (or their legally acceptable representative) must sign a separate informed consent form if he or she agrees to provide an optional DNA sample for research. Refusal to give consent/assent for the optional DNA research sample does not exclude a subject from participation in the study. Assent is also required of children capable of understanding the nature of the study (typically 7 years of age and older) as described in Section 16.2.3, Informed Consent and Assent form.

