The last dose of study agent is to be administered at the Week 52 study visit. Subjects will remain in the study until Week 104, continue recording data in their eDiary and followed for evaluations of safety, PK/anti-drug antibodies, and durability of response. Subjects will have assessments only at Week 78 and Week 104. All safety and efficacy assessments will be performed at these visits according to the [Time and Events Schedule](#). The visit windows for these 2 visits are \pm 10 days of the target visit day.

During the treatment and off-therapy follow-up periods subjects will continue to receive intensive management of their diabetes and maintain tight glycemic control according to the current ADA.⁶⁷

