9.9. Injection Site Reaction Monitoring

Injection reactions or allergic reactions have been observed with administration of monoclonal antibodies. Mild to serious local and systemic reactions (including anaphylaxis) may occur at any time during the administration of study agent.

Study agent must not be administered to individuals with known or suspected intolerance or hypersensitivity to any biologic medication or known allergies or clinically significant reactions to human proteins, to monoclonal antibodies or antibody fragments, or to any components of golimumab or its excipients.

A physician must be immediately available at the site during the first 3 dose administrations of study agent for the double-blind period and open-label extension period. All subjects receiving study agent must be carefully observed for symptoms of an injection site reaction and a systemic reaction for at least 30 minutes after study agent administration.

Injection Site Reactions

An injection site reaction is any unfavorable or unintended sign that occurs at the study agent injection site. If an injection site reaction is observed, the subject should be treated at the investigator's discretion. Any adverse reaction (eg, swelling, induration, redness/erythema, pain/tenderness, warmth, bruising or bleeding) should be recorded on the AE page of the CRF. The type of reaction should also be indicated.

Delayed Injection Site, Allergic, and Hypersensitivity Reactions

Reactions following study agent administration may occur 1 to 21 days after study agent injection and presentation can be variable, and can, for example include myalgia and/or arthralgia with fever and/or rash. In some cases, these may be accompanied by other symptoms including pruritus, localized or systemic edema, dysphagia, urticaria, sore throat, and/or headache. Any and all such adverse reactions should be recorded on the AE page of the CRF. The type of reaction should also be indicated.

Self-Assessment

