11.9. Safety Endpoints and Analyses

Safety assessments will include the examination of the incidence rates of AEs, vital signs, laboratory parameters, and physical examinations. Safety analyses will be conducted on the safety analysis set, which is defined as all subjects who have received at least a 1 dose of study agent.

Adverse Events

The verbatim terms used in the CRF by investigators to identify AEs will be coded using the Medical Dictionary for Regulatory Activities (MedDRA). Treatment-emergent AEs are AEs with onset during the treatment period or that are a consequence of a pre-existing condition that has worsened since baseline. All reported treatment-emergent AEs will be included in the analysis. For each AE, the percentage of subjects who experience at least 1 occurrence of the given event will be summarized by system organ class and preferred term for treatment group. Treatment-emergent AEs will also be summarized by a maximum severity and relationship to study agent. Separate summaries will be provided for SAEs and AEs leading to study agent discontinuation.

In addition, summary tables will be presented by treatment group for each of the endpoints within each specified period:

Double-Blind Period:

- a. Proportion of subjects with treatment-emergent AEs and severe AEs through Weeks 52 and 104.
- b. Proportion of subjects with study agent injection site reactions through Week 52.
- c. Proportion of subjects with severe infections through Weeks 52 and 104.
- d. Open-Label Extension Period:
 1. Continue to evaluate safety and exploratory efficacy endpoints as per the [Time and Events Schedule](#) (open-label extension period) and no new efficacy hypotheses will be tested compared to the double-blind period.

Listings, datasets, or subject narratives may be provided, as appropriate, for those subjects who die, who discontinue treatment due to an AE, or who experience a severe or an SAE.

Clinical Laboratory Tests

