1. INTRODUCTION

This statistical analysis plan (SAP) contains definitions of analysis sets, derived variables, and statistical methods for the analysis of efficacy, safety, pharmacokinetics, and immunogenicity of golimumab in the CNTO148DML2001 study. This SAP is specific to the Week 52 database lock (DBL).

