6.1. Adverse Events

The verbatim terms used in the CRF by investigators to identify adverse events will be coded using the Medical Dictionary for Regulatory Activities (MedDRA). Any AE starting at or after the initial administration of study agent through the end of the trial is considered to be treatment emergent. If the event occurs on the day of the initial administration of study agent, and either event time or time of administration are missing, then the event will be assumed to be treatment emergent. If the event date is recorded as partial or completely missing, then the event will be

considered to be treatment emergent unless it is known to be prior to the first administration of study agent based on partial onset date or resolution date.

All reported treatment-emergent adverse events will be included in the analysis. Treatment-emergent adverse events (TEAEs) by system organ class and preferred term (ie, number and proportion of subjects with one or more TEAEs within a system organ class) will be summarized by treatment group.

The following TEAE summary tables will be provided:

- Any TEAEs
- TEAEs by severity
- Serious treatment-emergent adverse event (SAEs)
- Reasonably related TEAEs
- Frequent TEAEs
- TEAEs leading to study agent discontinuation
- Injection site reactions
- TEAEs of special interest such as hypoglycemia events, infections, tuberculosis, malignancies

These summary tables will provide the count and percentage of subjects with 1 or more of the specified AEs by treatment group, and by system-organ class/preferred term respectively.

In order to support the additional assessment of particular categories of adverse events, additional summary is done on selected adverse events. The number and percent of subjects with the following selected TEAEs will be summarized by treatment group:

In addition to the summary tables, listings of subjects with the following AEs will be provided:

- Death
- Serious TEAEs
- TEAEs leading to discontinuation of study agent
- Hypoglycemia episodes reported as TEAEs
- Key Safety findings including malignancies, opportunistic infections, a new autoimmune disease or worsening of an existing autoimmune disease, and so forth.

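### The protocol's definition of treatment-emergent does not fit its own Week 104 adverse-event endpoint, and the differing SAP definition covers only the Week 52 lock

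*Protocol*

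**What the plan says.** The endpoint, "Proportion of participants with treatment-emergent AEs and severe AEs through Weeks 52 and 104", stands in Protocol Section 2.1 and is repeated in Sections 9.2.3 and 11.9.

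Protocol Section 11.9 gives the definition: "Treatment-emergent AEs are AEs with onset during the treatment period or that are a consequence of a pre-existing condition that has worsened since baseline". It does not say there what the treatment period is. Elsewhere the protocol describes a "52-week treatment period with study agent followed by a 52-week off-therapy follow-up period" (Synopsis and Section 3.1), and inclusion criterion 7 in Section 4.1.1 runs the treatment period from randomization to Week 52. Footnote d of the double-blind Time and Events Schedule starts the off-therapy phase after the Week 52 assessments and dose.

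SAP Section 6.1 defines the term differently: "Any AE starting at or after the initial administration of study agent through the end of the trial is considered to be treatment emergent". SAP Section 1 restricts that SAP to the Week 52 database lock.

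The injection-site-reaction endpoint in Protocol Section 2.1 runs through Week 52 only. Section 9.1.3.3 states: "The last dose of study agent is to be administered at the Week 52 study visit". Section 9.9 warns: "Reactions following study agent administration may occur 1 to 21 days after study agent injection".

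**The concern.** Section 3.2.1 of the protocol gives continued safety assessment as one reason for the off-therapy year. If the Section 11.9 definition is applied as written, an event that first appears in that year is not treatment-emergent. The Week 104 proportion could then exceed the Week 52 proportion only through worsened pre-existing conditions. A table showing little or no increase after Week 52 would partly reflect the definition and would be easy to misread as reassurance.

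The SAP wording does not settle the matter. It belongs to a plan for another lock, and it may be too broad for this endpoint. SAP Section 1.2 knows two database locks and no extension, whereas Protocol Section 3.1 plans three locks. Golimumab responders may restart open-label treatment provided they have not completed the Week 104 visit (Protocol Sections 4.2.2 and 9.1.5.1). If the trial ends with the extension, their re-treatment events would be counted too, and they would be added to the golimumab arm alone, because placebo responders cannot restart.

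**Working it through.** The plan states no adverse-event rate and no expected count, so it has no figure of its own to reproduce. The check is a comparison of definitions, followed by an illustration of size.

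**Step 1. What each definition counts towards the Week 104 proportion.**

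| Event | Protocol 11.9 | SAP 6.1 |
|---|---|---|
| New onset, first dose to Week 52 | counted | counted |
| Pre-existing condition worsening after Week 52 | counted (this part of the definition has no time limit) | counted if recorded as an AE starting then |
| New onset after Week 52, off therapy | not counted | counted |
| New onset after an open-label restart | unclear: the extension has its own treatment period | counted if the trial ends with the extension |

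The two definitions agree up to Week 52 for new-onset events. They part in the third row, which is what a Week 104 endpoint adds. The fourth row is settled by neither document, although Protocol Section 9.2.3.1 gives the extension its own safety endpoints.

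**Step 2. Possible size, by assumption.** Let p be the proportion with at least one event by Week 52. Assume the same constant hazard in both years, no dropout, and that all first events after Week 52 are new-onset. Then:

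- true proportion by Week 104 = 1 − (1 − p)²
- gap under the literal protocol definition = 1 − (1 − p)² − p = p(1 − p)

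| p at Week 52 | True value at Week 104 | Gap (points) | Of 54 on golimumab | Of 27 on placebo |
|---|---|---|---|---|
| 5% | 9.75% | 4.75 | 2.6 | 1.3 |
| 10% | 19% | 9 | 4.9 | 2.4 |
| 20% | 36% | 16 | 8.6 | 4.3 |
| 50% | 75% | 25 | 13.5 | 6.8 |
| 90% | 99% | 9 | 4.9 | 2.4 |

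The gap peaks at p = 50% and shrinks again when nearly everyone has had an event by Week 52. Under the SAP definition it is zero.

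**Step 3. Injection-site reactions.** The endpoint window ends at the Week 52 visit, and dose 27 of 27 is given at that visit. Planned time in the window after that dose is therefore 0 days, against the 1 to 21 days that Section 9.9 gives for delayed reactions. The ratio 1/27 = 3.7% is a share of doses, not an effect on the endpoint: the endpoint counts subjects, so only someone whose first reaction follows the last dose is missed.

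**The case against.** A reader might infer that the trial cannot count off-therapy events at all, or that off-therapy harms vanish from the report. The documents do not support that.

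- Protocol Section 11 calls itself a general description and leaves details to the SAP. The one SAP supplied uses a definition that includes the off-therapy year. A Week 104 SAP is not among the documents, and it may do the same.
- Section 11.9 itself lists the endpoint through Week 104, so its authors evidently expected later events to count.
- The worsening part of the definition has no time limit. In the endpoint's wording, severe AEs may also fall outside the treatment-emergent restriction; the phrase can be read either way.
- All adverse events are recorded until the last study procedure (Section 12.4.1). Severe infections have their own Week 104 endpoint without the treatment-emergent condition, and SAEs get a separate summary (Section 11.9). New malignancy, opportunistic infection and tuberculosis must be reported whenever they arise after the first dose (Section 12.4.4).
- Safety results are descriptive; SAP Section 6 plans no formal comparison.

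All of this stands, and it limits the consequence. It does not remove the conflict: the only definition whose scope reaches Week 104 excludes the events that this endpoint would add, and no supplied document says that another definition replaces it.

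On injection-site reactions, the objection is also partly right. The 21-day sentence covers allergic and hypersensitivity reactions as well as local ones, immediate reactions are caught by the 30-minute observation, and delayed ones still go on the AE page. A comparison with the extension is tempting but unsafe. Protocol Section 9.1.5.3 puts the last open-label dose at Week 50, which makes 50/2 + 1 = 26 two-weekly doses, while Section 7.1.1.1 states 27 and Section 9.1.5.1 lists OL Week 52 as a dosing visit. Those passages need reconciling in their own right.

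**Conclusion.** The concern holds as a conflict between definitions and should be corrected before the Week 104 analysis. Applied literally, Protocol Section 11.9 leaves new-onset off-therapy events out of the Week 104 treatment-emergent proportion. SAP Section 6.1 would include them, but it is scoped to another lock and, as worded, could sweep in open-label re-treatment.

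This is a defect in a reported proportion, not a loss of safety data. What is most exposed is new off-therapy events that are neither serious nor severe infections. The size cannot be derived from the documents. The range of about 5 to 25 points for Week 52 proportions of 5% to 50% rests wholly on the constant-hazard assumption; a lower event rate after treatment stops would make it smaller.

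The injection-site gap is real but minor: it concerns only first reactions that appear after the final dose.

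**What to change.** 1. In Protocol Section 11.9, define the Week 104 endpoint as adverse events with onset or worsening from first dose through Week 104, and say whether the restriction to treatment-emergent events applies to severe AEs.
2. Count events after an open-label restart in the extension only. Show off-therapy follow-up time by arm beside the proportions, because only golimumab subjects can have that time cut short by a restart.
3. Report Weeks 0 to 52 and after Week 52 through Week 104 separately. Section 2.1 already uses this split for hypoglycemia.
4. Carry the same definition into the Week 104 SAP and reconcile SAP Section 6.1 with it, replacing its open-ended reference to the end of the trial with a stated cut-off.
5. Extend the analysis window for injection-site reactions beyond the last dose, for instance by the 21 days named in Section 9.9.

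The cost is a few sentences and one or two table columns. No new data are needed, since adverse events are already collected through Week 104.

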2.2. Hypothesis

The primary hypothesis to be tested in this study is that golimumab is superior to placebo in maintaining β -cell function in children and young adults with newly diagnosed T1D as measured by MMTT-stimulated 4-hour C-peptide AUC at Week 52.

3. STUDY DESIGN AND RATIONALE

3.1. Overview of Study Design

This is a Phase 2a randomized, double-blind, placebo-controlled, parallel-group, multicenter, study of golimumab in subjects with new-onset T1D.

The duration of study participation will be 108 weeks, including screening and post-randomization. Following initial study screening, subjects must be randomized within 28 days. Following randomization there will be a double-blind 52-week treatment period with study agent followed by a 52-week off-therapy follow-up period.

Responders as defined below will be provided the option to participate in the 52-week open-label (OL) extension period.

The period to enroll all 81 subjects is expected to last approximately 12 to 18 months.

Schematic overviews of the double-blind study design and open-label extension period are provided in Figure 1 and Figure 2, respectively.

Figure 1: Schematic Overview of the Double-Blind Period

[figure not shown]
[figure not shown]

Figure 2: Overview of the Open-Label Extension Period

This study will enroll male and female subjects 6 through 21 years old who have been recently diagnosed with T1D. As described above (in Section 1) recent data indicate that the immunopathogenesis, disease progression and even response to immune therapies is different in younger population with T1D versus older adults. There is recent recognition by medical groups, diabetes experts and health authorities that it is important to conduct studies in children with T1D directly to best determine efficacy in T1D, as long as there is a known and acceptable safety profile.^{28,29,75} Additionally, the critical “prospect of benefit” of therapeutic TNF α -blockade in these younger individuals with new-onset T1D exists based on the aforementioned pilot trial described above conducted in children and adolescents.⁴⁸ The choice of the upper age cut-off of 21 years is based on studies noted above showing a differentiating break in disease progression and response to therapy at this age.^{25,27,61,75} Age 6 has been an accepted lower age threshold for enrollment in immunotherapeutic new-onset T1D studies, including those of abatacept and canakinumab.^{52,55} In addition there is a substantial amount of efficacy and safety experience of golimumab and other TNF α -blockers in children with other autoimmune diseases, and most of this is in those at and above 6 years old. This study will not enroll adults over 21 years old due to the difference noted above, including that there is not currently a “prospect of benefit” of anti-TNF α therapy in this older population. Most importantly as the goal for the sponsor is to develop a therapy for those who will most benefit from it, if older adults were to have a poorer response to therapy than younger individuals due to some of the reasons discussed above, this may result in diluting or missing important findings necessary to support further development in children, adolescents and young adults with T1D who are clearly those who have the most to gain from a disease modifying therapy.

Confirmation of the autoimmune nature of T1D in subjects will be determined by positivity of at least one T1D-associated autoantibody. Subjects must also show evidence of residual endogenous β -cell function, defined by a C-peptide level of ≥ 0.2 pmol/mL from a 4-hour MMTT at study screening, and be able to be randomized within 28 days of screening and 100 days of diagnosis.^{19,25,42,61}

A target of approximately 81 subjects will be randomly assigned in a 2:1 ratio to receive golimumab or placebo, administered SC for 52 weeks and monitored for an additional 52 weeks. Subjects will be randomized to receive active therapy (golimumab) or placebo and be stratified based on a C-peptide AUC of < 0.66 pmol/mL or ≥ 0.66 pmol/mL from a 4-hour MMTT conducted at study screening.

All randomized subjects will receive a total of 27 doses of study agent, either active treatment or matched placebo, administered SC every 2 weeks (q2w). Study subjects weighing < 45 kg who are randomized to active treatment will receive an induction dose of golimumab 60 mg/m^2 SC at Weeks 0 and 2 followed by a maintenance dose of 30 mg/m^2 SC at Week 4 and q2w through Week 52. Study subjects weighing ≥ 45 kg who are randomized to the golimumab treatment group will receive an induction dose of golimumab 100 mg SC at Weeks 0 and 2 followed by a maintenance dose of golimumab 50 mg SC at Week 4 and q2w through Week 52. Subjects randomized to the placebo treatment group will receive a SC placebo injection q2w through Week 52 to match the active arm (Figure 1). The protocol will give the option for study agent administration by subject or caregiver outside of the study site, ie, self-administration, after proper training (see Section 6).

Following randomization and the 52-week treatment period, there will be a 52-week off-therapy follow-up period focused on determining the off-therapy durability of the effect of golimumab. Thus, the participation for each subject is 104 weeks.

There will be a number of study visits that will include extensive metabolic assessments including a 4-hour MMTT. These assessments will occur at screening, during the double-blind treatment period (Weeks 12, 26, 38, and 52), and the off-therapy monitoring period (Weeks 78 and 104). The primary endpoint analysis will be derived from data obtained at the double-blind Week 52 visit (double-blind period). During the open-label extension period, a 4-hour MMTT will be performed during OL screening (unless performed < 3 months ago), OL Week 28, and OL Week 52. For C-responders who are lacking the necessary information to calculate IDAA1c score, an HbA1c will be performed and 10 days of insulin dose information will be required. Data from these and other visits will contribute to other key efficacy and safety endpoints and provide pharmacokinetic and exploratory assessments.

Three data base locks (DBLs) are planned for the study. The first DBL will occur after all subjects complete their Week 52 assessments (double-blind period), the second DBL will occur after the last subject completes the off-therapy follow-up period (Week 104), and the third DBL will occur after the last subject completes the open-label extension period.

An interim analysis based on 4-hour C-peptide AUC in response to an MMTT is planned for the study after at least 60% of subjects complete their Week 26 MMTT assessment. The primary goal of this interim analysis is to obtain an early read on treatment effect to facilitate planning of future studies.

During the study, all subjects will receive intensive management of their diabetes with exogenous insulin according to the current recommendations of the American Diabetes Association (ADA). Subjects and, when applicable, their caregivers must agree to follow the current ADA recommendations of tight glycemic control with specific HbA1c targets. These current recommendations are intended to achieve glucose levels that appear to decrease some of the short- and long-term sequelae of T1D. This study will include adhering to the ADA's recommended glycemic control guidelines with an HbA1c target of <7.5% in children 17 years old and younger and <7% in those 18 years old and above.⁶⁷ Approaches to achieve these HbA1c goals will be the responsibility of the subject, their caregivers and their health care providers.

Responders at Week 52 who are still in the follow-up period and who are determined to be in the active treatment group will have the option to restart active therapy while the non-responders will continue to follow the originally planned study design, ie, the off-therapy follow-up monitoring period.

There will be an open-label extension period of the study for responders. Responders are defined as subjects who have profile at Week 52 which includes:

1. C-peptide and Remission score* responders (C+R responders): either having an increase in C-peptide AUC versus baseline or having a stable C-peptide AUC, ie, not decreasing more than 5% versus baseline and having a remission score ≤ 9 .

OR

2. C-peptide responders (C responders): either having an increase in C-peptide AUC versus baseline or having a stable C-peptide AUC, not decreasing more than 5% versus baseline but not meeting a remission score of ≤ 9 . Their remission score, however, must be <12.

OR

3. Remission score responders (R responders): having a remission score ≤ 9 but not meeting C-peptide response as defined above. However, their C-peptide AUC decline from baseline should be less than or equal to 30% compared to baseline.

*Insulin Dose Adjusted HbA1c (IDAA1c) = A1C (percent) + [4 × insulin dose (units per kilogram per 24 h)].^{24,50,53,54}

An independent Data Monitoring Committee will be commissioned to continually assess the safety of study subjects. Refer to Section 11.11, Data Monitoring Committee, for details.

